### **Biosensor Arm:**

We will have a separate Biosensor Arm to allow for a wider range of naturalistic eating behavior data collection. Participants in the "Biosensor Arm" will wear the Garmin band and interact with the app for a 6-week period. This 6-week monitoring period can occur at any time (see **Biosensor Arm inclusion/exclusion)**. This will provide different insight into stress and eating behaviors and allow data to be collected on a wider range of participants. Participants will be provided with the Garmin band (Vivosmart 4), an Android phone with the app pre-loaded, and will follow the same procedures as described above (see **Procedures for Evaluating Naturalistic Eating Behavior and Stress with Wearable Biosensors**). The data management and statistical analysis will remain through the mHealth Core Facility at the University of Massachusetts as described above. The risks, data security & collection, and device information remain the same as the existing Biosensor piece.

The Biosensor Arm is identical to the Biosensor Portion of the main study. It is the same app. Participants do not have to be enrolled in the Main Study in order to participate in the Biosensor Arm.

Participants that did not complete the Biosensor as part of the main study while on medication, can now participate in the Biosensor Arm if interested. They will sign the Biosensor Consent Form in order to participate. Procedures will not be duplicated by any participant. The assessment table (Figure 2) lists the assessments completed in the Biosensor.

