4. **Research Plan:** Summarize the study design and research procedures using non-technical language that can be readily understood by someone outside the discipline. **Be sure to distinguish between standard of care vs.** research procedures when applicable, and include any flowcharts of visits specifying their individual times and lengths. Describe the setting in which the research will take place.

Overview of Study Design

This single-site, proof-of-concept, clinical trial is a double-blind, placebo-controlled, parallel group study to test the effectiveness of naltrexone + bupropion (NB) pharmacotherapy in BED patients with and without obesity. BED patients with (BMI > 30 and <50) and without obesity (BMI >21.5 and <29.9), will be randomized to NB (32 mg/day naltrexone combined with 360 mg/day bupropion) or placebo (n=50 per cell, n=200 total).

Following eligibility screening and randomization, participants will start a 12-week medication treatment period, a treatment period consistent with other BED medication trials (McElroy et al., 2016). Participants will have four weeks of up-titration: one tablet daily (Naltrexone 8mg/ Bupropion 90mg; 1 week), then two tablets daily (Naltrexone 16mg/ Bupropion 180mg; 1 week), then three tablets daily (Naltrexone 24mg/ Bupropion 270mg; 1 week), to reach the full dose of four tablets daily (Naltrexone 32mg/ Bupropion 360mg). The dosage will continue for the remainder of the 3 months. Medication will be discontinued at the end of 3 months, and patients will then be followed 12-months post-treatment to assess the durability of medication effects. The primary outcome measure is reduction in binge-eating frequency.

To evaluate correlates and mechanisms of NB on eating behavior, assessments will occur in the laboratory and in the field to optimize internal and external validity. Participants will complete human laboratory sessions ("lab sessions") before the start of medication and then during the final week of the 12-week medication period to evaluate the ability to resist eating preferred high-caloric food and subsequent overeating. During the laboratory sessions, we will evaluate potential mechanisms including eating peptides

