Monitoring Eating Behavior. During the 6-week monitoring period, we will monitor eating behavior in three ways through an app on the Android smartphone. 1) Participants will complete daily diaries every evening at 10PM or when participant initiates "End of Day" which assess eating throughout the day. Participants will answer questions about their daily eating pattern and stress. 2) Up to four times per day during waking hours, subjects will receive random prompts to assess whether they are currently eating or binge eating, as well as their stress. With these prompts, we will also be assessing GPS location, to determine medication response on these items when subjects are in various 'food-dense' environments (e.g., home, restaurant, neighborhood density of fast-food restaurants) 3) When subjects start to binge eat, they can initiate smartphone assessments assessing eating and stress. Additionally, they will complete an end-of-binge report that also assesses eating and stress.

The cell phone provided to participants will have the app already loaded and ready for use. The data that is input will be de-identified because it will be set up with a subject ID. This subject ID will be used to capture the data. UMass will not receive a "key" to identify the participants. This application does not qualify under the FDA definition as a medical device, and more specifically Software as a medical device ('FDA Software as a Medical Device (SAMD): Clinical Evaluation, Guidance for Industry and Food and Drug Administration Staff, issued on December 8, 2017'). Data collected from the app and the Garmin device will allow use to understand how stress affects your eating, and how the medication might affect this.

Data Management & Statistical Analysis: The mHealth Core Facility at the University of Massachusetts will assist with the collection of electronic data, transmitting and storage of the data, and providing collected and processed data to Yale. This data collection system (which integrates the Garmin Band data collection and the smartphone data collection) is being developed for the Yale-SCORE (HIC#2000023970; PI, [name]) and modified for this project. Statistical support for this project will be provided by biostatistician, [name].

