during the 12-month follow-up period. All possible interactions will be modeled and the following primary a priori contrast will be tested: 1) placebo NB vs. active NB. Least-square means will be plotted and compared post-hoc to interpret significant effects. Because we cannot a priori predict the shape of the response over time in each arm of the trial we will first treat time as a categorical predictor and will then test for polynomial trends over time. We will consider different error structures (e.g., AR1, CS, independence) and select the best fitting one based on Schwartz' Bayesian Criterion (BIC). We will compare dropout patterns between groups and if there are concerns of informative dropout or informative intermittent missing data, we will use pattern mixture models [93] to perform sensitivity analyses. Secondary models will include subjects with complete data. To test for assessment reactivity, we will evaluate whether biosensor assessment (yes/no; between-subject variable) moderates our primary outcomes in Aim 1 (as either a main effect, or interacting with medication). If this is found, then all subsequent analyses for Aims 1 & 2 will be limited to the sample (n=140) without the biosensor assessment.

Primary Aim 1. We will use the mixed models described above to test the effectiveness of NB medication for BED patients with and without obesity. The primary aims are to evaluate NB medication for (a) reducing binge eating frequency; and (b) in the patients with obesity, for reducing % weight loss. Significant NB main effects (regardless of obesity status) on frequency of binge eating will be considered supportive of our primary hypothesis. We also expect that NB will be associated with significantly greater reductions in % weight loss among the BED+obese group. In view of the factorial design, we will also be able to assess whether obesity status moderates reductions in binge eating frequency. These analyses will focus on 12-week outcomes. Secondary analysis will be repeated to examine change during the 12-month FU period.

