### SECTION III: RECRUITMENT/CONSENT AND ASSENT PROCEDURES

- 1. Targeted Enrollment: Give the number of subjects:
  - a. Targeted for enrollment at Yale for this protocol: N=200

b. If this is a multi-site study, give the total number of subjects targeted across all sites; n/a

77.0	, 0	•			
2. Indicate recruitment methods below.	Attach copies of any recruitment materials that	at will be used.			
		☐ Radio			
□ Posters	☐ Mass email solicitation	□ Telephone			
☐ Letter	☑ Departmental/Center website	□ Television			
☐ Medical record review*	☐ Departmental/Center research boards				
☐ Departmental/Center newsletters	☐ Web-based clinical trial registries	☑ Clinicaltrails.gov			
☑ YCCI Recruitment database	☐ Social Media (Twitter/Facebook):				
☐ Other: EPIC direct to patient					
* Requests for medical records should be made through JDAT as described at http://medicine.yale.edu/ycci/oncore/availableservices/datarequests/datarequests.aspx					

3. Recruitment Procedures:

a. Describe how potential subjects will be

	e identified.				
Participants will be recruited using ac	ds and flyers placed in local media (newspapers	and television), and			

recruitment and printed materials throughout the community. We will also work with YCCI using their recruitment strategies, including distribution of materials throughout the community, email and internet solicitation, working with community contacts, and receiving information about potential participants YCCI identified as interested in research related to our topics (obesity, binge eating disorder, mental and physical health).

**Biosensor Arm:** Participants who are interested in or currently enrolled in any study with the research team can be contacted to see if they are interested in participating in this Biosensor Study alone or in conjunction with the study they are currently enrolled in. Participants will follow the same screening, recruiting and consenting procedures as described below in person or remotely (i.e., Zoom). Participants enrolled in the study will be contacted and offered the biosensor arm. Participants not enrolled in the RCT will only be contacted if we have permission to contact them about future studies.

b. Describe how potential subjects are contacted.

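### The Biosensor Arm may place paid binge monitoring inside the 12-month durability follow-up, and the planned reactivity check is not built to handle it

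*Combined protocol and SAP*

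**What the plan says.** **Who may join, and when.** In Section I item 4, the Biosensor Arm text states: "This 6-week monitoring period can occur at any time", with a pointer to that arm's own eligibility criteria. It then admits trial participants: "Participants that did not complete the Biosensor as part of the main study while on medication, can now participate in the Biosensor Arm if interested". Section III item 3 makes this an active offer: "Participants enrolled in the study will be contacted and offered the biosensor arm". Participation may be "alone or in conjunction with the study they are currently enrolled in".

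**What the monitoring involves.** The arm uses the same app and procedures as the main-study biosensor component. Under Monitoring Eating Behavior, up to four times a day "subjects will receive random prompts to assess whether they are currently eating or binge eating". There is also an evening diary, a report when a binge starts and another when it ends. Section VI item 2 pays $6 a day for 42 days if prompts are answered, and up to $402 in all.

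**What follow-up is for.** Under Overview of Study Design, "patients will then be followed 12-months post-treatment to assess the durability of medication effects". Section I item 13 adds: "Secondary analysis will be repeated to examine change during the 12-month FU period". It also lists remission and relapse among the secondary outcomes. The Figure 2 grid places the EDE interview at baseline, month 3, 6 months and 12 months, and the Measures text gives it a 28-day focus.

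**The safeguard.** Section I item 13 says: "To test for assessment reactivity, we will evaluate whether biosensor assessment (yes/no; between-subject variable) moderates our primary outcomes in Aim 1". If moderation is found, later Aim 1 and Aim 2 analyses are confined to the 140 participants who did not have the biosensor.

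**The concern.** The plan takes seriously the possibility that binge monitoring changes binge eating. It tests for this and is ready to set aside 60 of 200 participants because of it. The Biosensor Arm then allows the same monitoring during the period that is meant to show what happens once medication stops.

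Uptake there is voluntary and comes after randomisation, so it may depend on how a participant is doing. If monitoring alters binge eating, the 6- and 12-month EDE counts of some participants would reflect monitoring as well as earlier treatment, and relapse rates within each arm could be off.

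The fallback is weakened as well. The sample it treats as unmonitored consists of the people who are later invited to be monitored.

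**Working it through.** **Reproducing the plan's own figures**

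- Sample without the biosensor: 200 randomised - 60 in the subset = 140, as in Section I item 13. The fallback therefore counts only the planned in-treatment subset.
- Biosensor Arm payment: 42 x $6 = $252; $252 + $25 + $25 + $100 = $402, as in Section VI item 2.

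**Does any text keep monitoring out of follow-up?**

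- Biosensor Arm exclusion 5 bars people now receiving effective treatment for eating or weight loss. Study medication has ended by follow-up.
- Exclusion 7 bars people in another study with current or future drug or device exposure. It could be read as barring trial participants, but the Biosensor Arm text and Section III item 3 expressly admit them.
- So neither exclusion protects follow-up. The wording about people who missed the biosensor while on medication points towards the off-drug period.

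**Does the reactivity check fit this exposure?** The factor is a single yes/no value per person. Someone first monitored eight months after treatment is unexposed at week 12 and at the 6-month EDE, and exposed at the 12-month EDE. Coding that person yes mislabels the earlier visits; coding no mislabels the last one.

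**How often could monitoring touch an EDE window?** The documents give neither uptake nor start dates, so this is an illustration. Assumptions: follow-up lasts 52 weeks; the EDE falls at weeks 26 and 52 after treatment; recall windows are weeks 22-26 and 48-52; monitoring lasts 6 weeks; the start is uniform over the permitted range. A start overlaps a window [a, b] if it lies between a - 6 and b.

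| Latest start allowed | 6-month window | 12-month window | Either |
|---|---|---|---|
| Week 46 (monitoring ends within follow-up) | (26 - 16)/46 = 21.7% | (46 - 42)/46 = 8.7% | 14/46 = 30.4% |
| Week 52 | (26 - 16)/52 = 19.2% | (52 - 42)/52 = 19.2% | 20/52 = 38.5% |

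The 12-month figure more than doubles with the choice of latest start, so it should be given as a range.

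**Numbers of participants**, with assumed uptake during follow-up among the 140:

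| Uptake | Monitored (share of 200) | Overlapping either window, at 30.4% to 38.5% |
|---|---|---|
| 10% | 14 (7%) | about 4 to 5 |
| 25% | 35 (17.5%) | about 11 to 13 |
| 50% | 70 (35%) | about 21 to 27 |
| 100% | 140 (70%) | about 43 to 54 |

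These count direct overlap only. An effect that outlasts the 6 weeks would reach more EDE values.

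**The case against.** **The check is repeated in follow-up.** Section I item 13 says all analyses are repeated over the 12-month follow-up. A reader might infer that follow-up has no reactivity check; the text does not support that. The repeat plausibly includes the check, and a late wearer could be coded yes. What remains is that a fixed between-subject factor suits an exposure starting partway through follow-up poorly, and that the fallback size of 140 shows only the planned subset was in mind.

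**The direction is not known.** A reader might infer that monitoring masks relapse and shrinks the difference between NB and placebo. The documents give no sign for reactivity: item 13 plans a test and asserts no effect. If participants who relapse after stopping NB took up monitoring and it helped, the difference would widen in favour of NB; if placebo participants did so more often, it would shrink. Participants and assessors stay blind through the 12-month assessment, so uptake cannot follow known allocation. With equal uptake and equal reactivity in both arms, the contrast is not biased.

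**Uptake driven by relapse is conjecture.** Staff make the approach, and lack of equipment is one stated reason for missing the biosensor during treatment. Voluntary uptake may still depend on clinical state, but the documents do not show that it does.

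**The size is assumed.** This stands. The wording of the offer suggests it was added later, so 140 is a ceiling.

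**Only secondary analyses are affected.** This also stands. The 12-week outcomes are primary and would be touched only if Biosensor Arm monitoring also fell within treatment.

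**Conclusion.** The concern holds in a limited form. The protocol allows monitoring that it treats as possibly reactive to fall within the durability follow-up, with no protected period around the 6- and 12-month EDE and no analysis suited to exposure that begins during follow-up.

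What could be contaminated is the secondary evidence on durability and relapse. Within-arm relapse rates may be affected whether or not the arms differ in uptake. The contrast between NB and placebo is biased only if uptake or reactivity differs by arm. Direction and size cannot be determined from the documents; the overlap percentages rest on assumed uniform starts and assumed visit weeks, and the counts on assumed uptake.

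The point does not call the 12-week primary result into question. It merits correction because follow-up serves a stated purpose of the trial and the change is small.

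**What to change.** 1. **Timing.** In the Biosensor Arm text of Section I item 4 and in Section III item 3, state that randomised participants are offered the arm only after their 12-month EDE is complete. Reconcile Biosensor Arm exclusion 7 with that text.
2. **Participants already monitored.** Take start and stop dates from the device and app records. Enter monitoring as a time-varying exposure in the follow-up models, and report uptake by treatment arm. Because uptake follows randomisation, show this model beside the planned intent-to-treat analysis, not in its place.
3. **Fallback sample.** If reactivity is found, define the sample without the biosensor by actual exposure instead of a fixed 140. Do not simply delete EDE values obtained after monitoring began: if relapse prompts uptake, deletion would selectively remove relapses.

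The cost is one sentence in each of two places and a short addition to Section I item 13. The downside is that trial participants would enter the Biosensor Arm later, and perhaps in smaller numbers. The arm stays open to people outside the trial.

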### Assessments:

Participants will complete baseline assessments prior to starting the 6-week monitoring period. These assessments will help to identify possible eating disorder psychopathology and provide baseline information for stress and eating behaviors (i.e., EDE-Q/PSS). Participants will then complete the assessments at the end of the 6-week monitoring period.

Specific inclusion/exclusion criteria for the biosensor arm are listed in the inclusion/exclusion section of the protocol.

# Assessments.

Figure 2. Grid depicting when each assessment is obtained

rigare 2. Oria acpioning	when each assessment is obtained		Р	RE	DURING TREATMENT			Follo	OW-UP			
MEASURE	INSTRUMENT AND REFERENCES	Түре	BASELINE	LAB #1	WEEK 2	MONTH 1	MONTH 2	MONTH 3	LAB #2	6 Момтн	12 Month	BIOSENSOR
Screening Measures							ı		1			
Axis I Disorders	MINI Psychiatric Interview	Interview	*									
Binge-Eating Disorder	EDE Interview	Interview	*					*		*	*	
BMI	Weight, height	RA Eval	*	*	*	*	*	*	*	*	*	
Metabolic Measures	Lipids, HbA1c TSH (as needed)	Blood	*	*					*	*	*	
Safety Measures	Urine screen for pregnancy Urine drug test for opiates	Urine	*									
Menstrual Cycle Data	Menstrual cycle calendar, hormone use, reproductive and gynecological status	Interview	*		*	*	*	*		*	*	
Medical History	Clinical data, incl. start of new treatments	Interview	*					*			*	
Eating Behavior & Food C	Craving											
Eating Disorders	EDE-Q ELOCS	Self-Report	*		*	*	*	*		*	*	*
Eating Behavior	TFEQ YFAS	Self-Report	*			*	*	*		*	*	
Food Craving	Brief Questionnaire of Food Craving FCI-II	Self-Report	*	*		*	*	*	*	*	*	
Drive for Palatable Food	PFS Control of Eating Questionnaire	Self-Report	*	*		*	*	*	*	*	*	
Hunger	Hunger Ratings	Self-Report		*					*			
	Health and Behaviors	0 16 5	*		*	*	*	*	 	*	*	
Depression	Beck Depression Inventory-II	Self-Report	*	*	*	*	*	*	*	*	*	
Affect	Circumplex Scale	Self-Report		Î					Ŷ			+
Quality of Life	Perceived Stress Scale	Self-Report	*			-		*			*	*
Quality of Life	SF-12 Audit-2	Self-Report	*					*			*	
Alcohol Use	Godin Leisure Time Exercise Questionnaire	Self-Report	*					*			*	
Physical Activity Sleep		Self-Report	*	-		-		*			*	
Sieep	Pittsburgh Sleep Quality Index	Self-Report										
Safety & Compliance								 				
Adverse Events	SAFTEE Columbia Suicide Severity Rating Scale	Interview			*	*	*	*				
	Liver Function	Blood		*		*			*			

Page **12** of **49** 

Medication Compliance	Pill Counts	RA Count						*				
	Naltrexone and Bupropion levels	Plasma				*		*				
Vitals	Blood pressure and heart rate		*	*	*	*	*	*	*	*	*	
Placebo Rating	Placebo rating by clinician and participant	Self-Report				*		*				
Assays												
	Leptin, ghrelin, estrogen, progesterone	Blood		*					*			

### Measures:

### **Screening Measures**

- MINI International Neuropsychiatric Interview-Version 7.0 (MINI) [57] is a brief structured interview for Axis I psychiatric disorders. Validation and reliability studies have supported the MINI, including good convergence with SCID [57]. The MINI requires much less time than the SCID and reduces participant burden while providing adequate psychiatric data to characterize patients and determine exclusion criteria.
- Eating Disorder Examination Interview—16th Edition (EDE) [58] is an investigator-based interview assesses the features of eating disorders and generates eating disorder diagnoses. The EDE will be our primary method for assessing binge eating and eating disorder psychopathology. The EDE focuses on the previous 28 days, except for diagnostic items, which are rated for additional duration stipulations to address *DSM*-5 criteria for BED. The EDE assesses the frequency of different forms of overeating, including objective binge-eating episodes (OBE; i.e., unusually large amounts of food with loss of control). The EDE also comprises four scales (dietary restraint, eating concerns, weight concern, and shape concern) and a global severity score. The EDE has good psychometric properties [59], is the major outcome measure for BED RCTs [44, 60], and has good test-retest reliability.
- Body Mass Index (BMI) will be calculated using measured Height (measured once at baseline) and Weight (obtained regularly at assessment meetings).
- Lipid profiles (**Lipids**): total cholesterol, HDL-, LDL-cholesterol, triglycerides will be obtained fasting per established protocols (Anderson et al., 1995).
- Glycemic Control: HbA1c, Glucose and Mean Plasma Glucose, routine measures of average glucose control for a previous (3-month) period.
- Hepatic function panel (**Liver Function**) will be assessed for safety at the first monthly treatment visit and at the end of treatment.
- Thyroid-stimulating hormone (TSH) will be assessed if patients report any history of thyroid disease or are taking thyroid medications.
- Urine drug testing for opiates will be completed for all participants.
- Urine pregnancy testing will be assessed for female patients of child-bearing potential.
- Menstrual Cycle Data: Menstrual cycle calendar (updated regularly), hormone use, reproductive and gynecological status
- We will also gather sociodemographic information and clinical data on the patient's medical history and comorbidities prior to the study, which we will update as indicated. If patients begin other treatments, this will allow us to account for this in analyses.

